The study included a total of 32 volunteers between the ages of 65-80, who stayed in Karaman Ahmet Mete Nursing Home, Elderly Care and Rehabilitation Center, with mild or moderate Alzheimer's dementia diagnosed by a neurologist. There were 90 older people in Karaman Ahmet Mete Nursing Home, Elderly Care and Rehabilitation Center. Power analysis was performed to determine the size of the sample to be included in the study. As a result of the power analysis, assuming that the effect size to be obtained between the two groups will be large ($d = 0.9$), when at least 32 individuals (at least 16 individuals per group) were included in the study, it was calculated that 80% power could be obtained at 95% confidence level (with 0.05 error margin). As a result of the power analysis, it was calculated that at least 16 individuals could be included in each group (at least 32 individuals in total). 20% risk rate was determined for the individuals who could leave the study, 3 individuals were added to each group, and the study was organized with 19 individuals in each group. However, these people were excluded from the study as 4 people were not meeting inclusion criteria, 2 people were declined to participate, and therefore the study was completed with 32 individuals (Figure 1). The study included volunteers between the ages of 65-80 with mild or moderate AD diagnosis, who did not have any difficulty or problems in communicating, who did not have any neurological diseases that disrupt balance and coordination such as a cerebrovascular event, Parkinson's disease, Multiple Sclerosis, and neurological disorder, who obtained a score of 18 - 24 points in the Mini-Mental State Test (MMST) were included in the study. Patients diagnosed with rapidly progressing dementia (infection, vascular, hematologic diseases), those who could not be contacted during the follow-up period or who did not participate in the training session, those who experienced cardiac and cerebrovascular events, endocrine disorders, fluid-electrolyte imbalance and infection, those with malignancy and those who received chemotherapy and radiotherapy that causes malignancy, delirium or depression and malignant sensory loss (those with the Semmes-Weinstein monofilament thickness of 4.56 and above), and those with a lower or upper extremity amputation at any level were excluded from the study.

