Muscle strength was evaluated by the knee extension strength. The knee extension strength was measured by a hand-held muscle strength dynamometer (Baseline Evaluation System, New York). The knee extension strength measurement was preferred in this study because it is a measurement that gives information about general lower extremity muscle strength. The knee extension strength was evaluated in the sitting position with the hip and knee joint at 90° flexion. The patient was asked to arrange his/her leg, the force was applied over the ankle, and the patient was asked to resist this force and keep his/her position. This measurement was repeated 3 times bilaterally, and the arithmetic mean of the values was taken. This

measurement was performed twice as the first and last evaluation, and the results were recorded in kg-force [24].

The fall was evaluated with the Tinetti Falls Efficacy Scale (TFES), and this scale is a 10-item scale. These items include bathing, reaching out to shelves, walking inside the house, preparing food, going to bed and getting out of bed, answering the door, sitting on the chair and getting up from the chair, getting dressed and undressed, personal care, going to the toilet and leaving the toilet. The question of “How much do you feel confident while doing the above activities?” was asked to state a point between 1 and 10. 1 means very high confidence, and 10 means no confidence. A score between 0 and 100 is obtained in total. If the total score is more than 70 points, there is fear of falling.

[figure not shown]
The Timed Up and Go Test (TUG) is a test that assesses the fall risk, mobility and physical performance in older people. A chair and a stopwatch are required to perform the test. The test is carried out with the patient's usual shoes, and the patient is told that he/she can use walking aids if needed. This test was performed by giving the command to the individual to get up from the chair without arm support while sitting on the chair, to walk in a predetermined 3-meter area and return, and to sit again on the chair without arm support (Image 3.1). The result was recorded in seconds (sec). If the older people completes this test in a longer time than 12 seconds, there is a fall risk.

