The data were analyzed using the SPSS 24.0 packaged software. Continuous variables were presented as mean \pm standard deviation, median (minimum and maximum values), while categorical variables as number and percentage. The suitability of the data for normal distribution was examined by the Shapiro-Wilk test. The significance test of the difference between the two means was used in comparing the independent group differences when the parametric test assumptions were provided, and the Mann-Whitney U test was used in comparing the independent group differences when the parametric test assumptions were not provided. The significance test of the difference between the two pairs was used in comparing the dependent group differences when the parametric test assumptions were provided, and the Wilcoxon two-pPaired sample test was used when the parametric test assumptions were not provided. Differences between categorical variables were analyzed by chi-square analysis. In all analyses, $p<0.05$ was accepted as statistically significant.

Results

The mean age of the individuals was 73.13 ± 3.54 years, and the mean age of the training group was 73.75 ± 5.16 years. No statistically significant difference was found between the groups in terms of age, gender, height, weight, body mass index, occupation, marital status, education level, income level, number of children, and social security ($p>0.05$).

Upon examining the MMST values, the difference between the 2 groups was not statistically significant ($p>0.05$). In the post-training measurements, the values of the training group were significantly higher compared to the control group ($p<0.05$). When the changes in the groups before and after the training were examined, no statistically significant change was observed in the control group, whereas the values of the training group were significantly higher after the treatment ($p<0.05$).

When the right and left knee extension muscle strength values of individuals with AD were examined, the difference between the 2 groups was not statistically significant before and after the training ($p>0.05$). When the changes of the groups before and after the training were examined, there was no significant change in the control group, whereas the values of the training group were significantly higher after the training ($p<0.05$).

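### Knee-extension strength stands for general leg strength but is tested separately for right and left; one bilateral mean per participant would fit the stated question better, usually with a little less noise

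*Combined protocol and SAP*

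**What the plan says.** The Abstract names muscle strength and fall risk as the two things the training is meant to change. The Study Procedure and Protocol section chooses knee extension because "it is a measurement that gives information about general lower extremity muscle strength". Readings were taken with a hand-held dynamometer in kg-force: "This measurement was repeated 3 times bilaterally, and the arithmetic mean of the values was taken". That sentence can mean three readings averaged within each leg, or all six averaged into one figure.

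The Statistical Analysis Plan defines no strength variable. It gives a generic choice between parametric and rank tests, for comparisons between groups and within groups, and one threshold: "In all analyses, $p<0.05$ was accepted as statistically significant". It has no rule for combining two legs or for handling two strength tests. The strength paragraph of the Results begins "When the right and left knee extension muscle strength values of individuals with AD were examined" and reports no significant between-group difference before or after training, with a significant rise within the training group only.

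No side-specific aim appears. All trained participants played the same games. Dominant side is recorded on the case report form, but no analysis is said to use it.

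**The concern.** The stated rationale describes one quantity per person, general lower-limb strength. The analysis yields two correlated measurements of it, neither named as decisive. Two things follow.

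- **Precision.** Each single-leg comparison uses half of the readings and carries leg-specific measurement error that averaging the legs would partly remove. In a trial of 32 people with a non-significant between-group result on a main target, that is information already collected and not used.
- **Interpretation.** Two tests at 5% with no decision rule leave open what counts as a positive strength result: either leg, both legs, or one in particular. The Abstract concludes that training increased muscle strength, and no single between-group estimate stands against that conclusion.

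**Working it through.** **1. Inputs.** From the sample size paragraph of the Study Procedure and Protocol section: d = 0.9, 80% power, 0.05 level, "at least 16 individuals per group". Sidedness is not stated. From the Results: right and left are reported separately. Not in the documents, and therefore assumed: the right-left correlation r, equal SDs on the two legs, and the same effect on both.

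**2. The plan's own figure.** For a two-sample t-test with d = 0.9 and 16 per arm (noncentral t, 30 degrees of freedom, level 0.05), power is 80.0% one-sided and 69.3% two-sided. For 80% power, 16 per arm are needed one-sided and 21 two-sided. The stated 16 therefore reproduces only as a one-sided calculation. That is a separate matter; two-sided power is used below. The planning d is not tied to strength or to any other named outcome, so 0.9 serves only as an illustration.

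**3. Effect of averaging the legs.** If each leg has SD s, the bilateral mean has variance s²(1+r)/2. Its SD is s × sqrt((1+r)/2), and the standardised effect becomes d / sqrt((1+r)/2). For example, at r = 0.8, sqrt(1.8/2) = 0.949 and 0.9/0.949 = 0.949.

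| r (assumed) | SD ratio | d for mean, per-leg 0.9 | Power | Power if per-leg d = 0.5 |
|---|---|---|---|---|
| one leg only | 1.000 | 0.900 | 69.3% | 27.8% |
| 0.6 | 0.894 | 1.006 | 78.6% | 33.4% |
| 0.8 | 0.949 | 0.949 | 73.8% | 30.3% |
| 0.9 | 0.975 | 0.923 | 71.5% | 29.0% |
| 0.95 | 0.987 | 0.911 | 70.4% | 28.4% |

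The gain at d = 0.9 is about 9 points at r = 0.6, 4 to 5 at 0.8, 2 at 0.9 and 1 at 0.95. At d = 0.5 it is about 6 points or fewer over the same range.

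**4. Two tests against one.** Simulated at 16 per arm, 50,000 trials for each r, each test two-sided at 5%:

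| r | False positive on at least one leg (no effect) | Power, both legs (d = 0.9) | Power, either leg (d = 0.9) | Power, bilateral mean (d = 0.9) |
|---|---|---|---|---|
| 0.5 | 9.2% | 54.9% | 84.0% | 81.2% |
| 0.8 | 7.9% | 60.1% | 78.6% | 73.7% |
| 0.95 | 6.4% | 64.6% | 73.6% | 70.3% |

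Requiring both legs costs power. Accepting either leg gains power only by exceeding 5%. The bilateral mean stays at 5% and lies between the two.

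**5. Unequal SDs.** Let the quieter leg have SD 1 and the other k, with the same effect in kg-force. The mean has variance (1 + k² + 2rk)/4, which exceeds 1 when k² + 2rk > 3. That happens for k above about 1.23 (r = 0.6), 1.11 (0.8) or 1.05 (0.9). At k = 1.2 and r = 0.9 the variance is (1 + 1.44 + 2.16)/4 = 1.15, so d falls from 0.9 to 0.9/1.072 = 0.839 and power from 69% to 63%. The noisier leg alone would have d = 0.9/1.2 = 0.75 and power of 54%.

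**The case against.** **The wording does not prove a mismatch.** A reader might infer that the protocol promised one value per person and that the Results contradict it. The documents do not support that. The sentence reads equally well as three trials averaged within each leg, and the right and left reporting fits that reading. What stands is that the wording must be settled and that, on either reading, no reported comparison uses a general-strength value.

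**The gain may be very small.** No correlation, SD or strength p-value is given. If each leg is already a mean of three trials, part of the trial error has gone. At r of 0.9 or more the gain is 1 to 2 power points. This stands, and it limits the size of the point.

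**Averaging is not free of loss.** A reader might infer that it can never hurt if the effect is the same on both legs. That also needs similar SDs, as step 5 shows. An effect confined to one leg would be diluted. Both caveats stand. However, the documents hypothesise no such effect and give no basis for choosing the quieter leg in advance.

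**No conclusion is shown to be distorted.** Both legs are reported with the same pattern, and no favourable side was picked. The strength conclusion rests on within-group change, and redefining the outcome does not repair that inference. This stands.

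**The change comes after the results.** The date list in the document places the statistical analysis in May 2018. Redefining an outcome once its per-leg comparisons are known to be non-significant is result-aware and must be disclosed as such.

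**Conclusion.** The point holds as an inexpensive improvement to the outcome definition. Knee extension stands for general leg strength, both legs were read, no side-specific question is stated, and the two legs are tested separately with no rule for combining them. A single bilateral mean matches the stated construct and gives one estimate and one 5% test, in place of two tests with a combined false-positive chance of about 6% to 9% (r from 0.95 down to 0.5).

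The precision benefit is secondary and uncertain. At per-leg d = 0.9, two-sided power rises by about 1 to 9 points for r between 0.95 and 0.6. This rests on similar SDs, a common effect on both legs and an assumed r. A reader might infer that the between-group strength comparison missed significance because the legs were split, or that averaging would make it significant. Nothing in the documents supports either inference.

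**What to change.** In the Study Procedure and Protocol section, state how readings become a value: three per leg averaged within the leg, then right and left averaged, giving one figure in kg-force per participant and visit (six readings). In the Statistical Analysis Plan, name this as the strength outcome and base the between-group strength comparison and the strength conclusion on it. Report right and left as supportive results, with their SDs and the right-left correlation, so that readers can judge how much averaging gained and whether the legs differ in variability.

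The cost is a few sentences and one re-run on existing data. The re-run must be labelled post hoc, with a statement that the per-leg results were known when the outcome was redefined, and the per-leg results already reported should stay visible. The price is that an effect confined to one leg would be diluted in the main strength result and would show only in the supportive figures.

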Results: The mean age of the control group was 73.13 ± 3.54 years, and the mean age of the training group was 73.75 ± 5.16 years. In the statistical analysis between groups, the Mini-Mental State Test values were found to be statistically significant in favor of the training group ($p=0.049$). In the intra-group statistical analysis, there was a significant difference in all tests in the training group after the training, while no significant difference was found in the control group.

Conclusions: It was found out that the virtual reality application in individuals with Alzheimer's dementia increased muscle strength and decreased the fall risk. As a result, supporting the physiotherapy and rehabilitation programs with technological developments and virtual reality applications will increase the success of the treatment.

Keywords: Alzheimer's Dementia; Muscle strength; Fall; Virtual reality

Study Procedure and Protocol

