When the TFES values were examined, no difference was found between the 2 groups before and after the training ($p>0.05$). When the changes of the groups before and after the training were examined, there was no significant change in the control group ($p>0.05$), whereas the values of the training group were significantly lower after the training ($p<0.05$).

When the TUG test values were examined, there was no difference between the 2 groups before and after the training ($p>0.05$). When the changes of the groups before and after the training were examined, there was no significant change in the control group ($p>0.05$), whereas the values of the training group were significantly lower after the training ($p<0.05$).

Conclusion

Along with cognitive functions, losses in motor functions such as muscle strength, balance, coordination, and walking occur in individuals with AD. A good physiotherapy and rehabilitation program is required to prevent and treat these problems. The virtual reality environment is a computer-generated three-dimensional simulation of a real-world situation in which the user can sense and control this simulation environment sensorially by means of special devices. In conclusion, the support of physiotherapy and rehabilitation programs with technological developments and virtual reality applications will increase the success of treatment especially for muscle strength, walking speed, reduction of fall risk and cognitive functions. This training may work as well, and that the results indicate that it may reduce the risk of falls.

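### The Tinetti Falls Efficacy Scale measures fear of falling by its own scoring, so it cannot support the conclusion that training lowered fall risk; only the Timed Up and Go Test can, and it showed no between-group difference

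*Combined protocol and SAP*

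**What the plan says.** The Abstract (Purpose) gives the trial two targets, muscle strength and fall risk. The section Study Procedure and Protocol introduces the TFES with "The fall was evaluated with the Tinetti Falls Efficacy Scale (TFES), and this scale is a 10-item scale". The same paragraph gives the question put to participants, "How much do you feel confident while doing the above activities", the anchors, "1 means very high confidence, and 10 means no confidence", and the interpretation, "If the total score is more than 70 points, there is fear of falling".

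The next measure in that section is introduced differently: "The Timed Up and Go Test (TUG) is a test that assesses the fall risk, mobility and physical performance in older people". A TUG time above 12 seconds is taken to mean that fall risk is present.

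Falls themselves appear once, as a count over the preceding year on the sociodemographic form. No count during the six weeks is described as an outcome.

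The Abstract (Conclusions) says that training "increased muscle strength and decreased the fall risk". The closing Conclusion section returns to fall risk twice, once firmly and once in hedged terms. On the TFES, the Results section reports: "When the TFES values were examined, no difference was found between the 2 groups before and after the training" (p>0.05). It reports the same for TUG. Both scores fell significantly within the training group and did not change significantly in the control group.

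**The concern.** The plan labels a confidence score as the evaluation of falls. A reader who takes the label at face value will think that falls, or the risk of them, were measured by two instruments, and will count a lower TFES total as evidence on the second aim. By the document's own anchors, a lower total shows that participants felt more confident. Nothing in the document links a TFES total to falls or to fall risk.

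The way the score is obtained is a further reason to keep it apart. It is a self-rating, and the control group received no training during the six weeks, so participants necessarily knew which arm they were in. At stake is whether one of only two aims may be declared met.

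**Working it through.** This is mainly a question of what each outcome measures, so the descriptions are set side by side. All come from Study Procedure and Protocol, except the last two rows, which come from Results.

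| | TFES | TUG |
|---|---|---|
| Introduced as measuring | the fall | fall risk, mobility, physical performance |
| What is recorded | self-rated confidence, ten activities | seconds to complete the test |
| Cut-off | above 70 | above 12 seconds |
| Cut-off is said to mean | fear of falling | fall risk |
| Change within training group | lower, p<0.05 | lower, p<0.05 |
| Between groups, before and after | p>0.05 | p>0.05 |

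**Step 1: construct.** In the TFES column the first row disagrees with the second and fourth: the label says falls, while the question and cut-off say confidence and fear. The TUG column is consistent. The document therefore has two cut-offs for two different things, and only one of them is fall risk.

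**Step 2: which outcomes can bear on the aim.** Of the four measures, the Mini-Mental State Test is assigned to cognition and dynamometry to strength. That leaves TFES and TUG. Step 1 removes the TFES, so TUG remains.

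**Step 3: what TUG shows.** It fell within the training group only, and the groups did not differ after training (p>0.05). A significant change in one arm and a non-significant change in the other is not a comparison of the arms.

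**Step 4: what p>0.05 can bear.** The plan assumes d = 0.9, 16 per group, alpha 0.05 and 80% power. Inputs to the noncentral t: noncentrality = d × √(n/2) = 0.9 × √(16/2) = 2.546, with 2 × 16 − 2 = 30 degrees of freedom. This gives power of 80.0% one-sided, which reproduces the plan's figure, and 69.3% two-sided. The plan states neither the sidedness nor the outcome to which d = 0.9 refers. If it applied to TUG with a two-sided test, a true effect of that size would be missed with probability 100% − 69.3% = 30.7%. The result is therefore not shown, rather than shown to be absent.

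**Side check on the scoring.** The text says "A score between 0 and 100 is obtained in total". Ten items scored 1 to 10 give 10 × 1 = 10 to 10 × 10 = 100. The lower limit does not fit the items. The point above does not depend on this.

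**The case against.** The strongest reply is that this is one loose phrase. The same paragraph gives the scale's full name, its confidence question and its fear-of-falling cut-off; the next makes TUG the fall-risk test; and Results reports the two separately without calling the TFES fall risk. Nowhere does the document say that its fall-risk conclusion rests on the TFES, so the conclusion may rest on TUG alone.

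Much of that stands. A reader might infer that the conclusion was drawn from the TFES, and the document does not establish this. A reader might also infer that the conclusion has no basis at all; that is too strong, because TUG is defined as a fall-risk test and did fall in the training group.

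It is also fair to say that relabelling alone changes little. Neither measure differed between groups, so between-group support is absent under either label. Drawing a conclusion from a change in one arm is a separate fault, and it affects muscle strength as well.

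What the reply does not remove is the conflict between the label and the scoring, or the fact that the label invites the TFES result to be read as evidence on a stated aim. Once the TFES is set aside, the conclusion has to be judged on TUG, and the between-group TUG result does not support it.

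**Conclusion.** The point holds. As the document describes it, the TFES measures confidence and fear of falling and cannot support a statement about fall risk. TUG can, but it showed no between-group difference after training (p>0.05). There is no corrected number; the size of the point is that the second of two stated aims cannot be reported as achieved.

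This rests on the document's own definitions and reported results, and on reading the conclusion as a claim about the effect of training, which needs a comparison with the control group.

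Four stronger readings are not supported:
- That falls during the trial were definitely not counted. The document only describes no such count as an outcome.
- That the assessments were unblinded throughout. Participants knew their arm, but assessor blinding is not stated, and a different physiotherapist from the trainer did the evaluations.
- That training has no effect on fall risk. A non-significant result with 16 per group does not show this.
- That confidence and fall risk diverge in people with dementia. The document gives no evidence on this, and the point does not use it.

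**What to change.** In Study Procedure and Protocol, describe the TFES as a measure of falls efficacy or fear of falling, and name TUG as the fall-risk measure. Correct or explain the stated score range at the same time.

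In the Statistical Analysis Plan, state that any conclusion about fall risk rests on the between-group TUG comparison.

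In the Abstract and Conclusion, replace the statement that fall risk decreased with two separate ones: TUG time improved within the training group with no significant between-group difference shown, and fear of falling (TFES) improved within the training group with no significant between-group difference shown. Bring the fall-risk sentences in the closing Conclusion into line.

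No new data or analysis is needed. The cost is rewording and a weaker claim on the second aim.

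### Arms are compared by a t-test or Mann-Whitney test chosen by Shapiro-Wilk, without using baseline; one ANCOVA per outcome would be more precise, and the test behind MMST p = 0.049 should be named

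*Combined protocol and SAP*

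**What the plan says.** The Statistical Analysis Plan begins with a normality check: "The suitability of the data for normal distribution was examined by the Shapiro-Wilk test". If parametric assumptions are met, the arms are compared by a test of the difference between two means, which I read as the t-test. Otherwise, "the Mann-Whitney U test was used in comparing the independent group differences when the parametric test assumptions were not provided". The paired comparisons switch in the same way: "the Wilcoxon two-pPaired sample test was used when the parametric test assumptions were not provided". The significance level is common to all: "In all analyses, $p<0.05$ was accepted as statistically significant".

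The plan does not give the Shapiro-Wilk threshold. It does not say whether the check is applied to each arm, to pooled data or to changes, or whether tests are two-sided. It plans no baseline-adjusted model and no between-arm difference with a confidence interval.

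Under Study Procedure and Protocol, first evaluations took place before randomization, and 32 people were allocated 16 to 16. In the Abstract, "the Mini-Mental State Test values were found to be statistically significant in favor of the training group", with p = 0.049. The Results section places that difference in the post-training scores. Between-arm comparisons of knee strength, the Tinetti Falls Efficacy Scale (TFES) and Timed Up and Go (TUG) all have p > 0.05.

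**The concern.** A test chosen by a pre-test on 16 people per arm depends partly on the sample drawn. The two candidate tests ask different questions (means versus distributions) and can fall on opposite sides of 0.05 when the result is borderline, as 0.049 is. Because the trigger is not fully specified, two analysts following the same plan could pick different tests.

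The larger loss is that every participant has a baseline value and neither between-arm test uses it. In a trial this small, that information could narrow the interval for every outcome. At stake are the precision of all between-arm comparisons and how far the single significant one can be relied on.

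**Working it through.** **1. The plan's own figure.** The inputs from Study Procedure and Protocol are d = 0.9, 80% power and a 0.05 error level, giving 16 per group. The normal-approximation formula is n = 2(z_alpha + z_beta)²/d².
- One-sided: 2(1.645 + 0.842)²/0.81 = 15.3, so 16. The exact t-test power at 16 is 0.800, so the stated figure reproduces.
- Two-sided: 2(1.960 + 0.842)²/0.81 = 19.4, so 20 (21 by the exact t calculation). Power at 16 is 0.693.

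The documents do not state sidedness. This matters here because a two-sided unadjusted comparison has little precision to spare.

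**2. How often the rule switches.** Assumption: Shapiro-Wilk at 0.05 in each arm, with rejection in either arm leading to Mann-Whitney. If one arm is flagged with probability q, the switch probability is 1 − (1 − q)². For normal data, q = 0.05 gives 1 − 0.95² = 0.098. Simulation used 16 per arm and 20,000 null trials per distribution:

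| Assumed distribution | Switch to Mann-Whitney | Type I error of two-stage rule |
|---|---|---|
| Normal | 10% | 0.049 |
| Integer MMST-like, 18–24 | 35% | 0.050 |
| t, 3 df | 49% | 0.051 |
| Lognormal, sigma 0.5 | 66% | 0.052 |
| Exponential | 92% | 0.050 |

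Other simulations with different assumed distributions gave at most 0.056. The branch taken varies from sample to sample, but the error rate stays close to nominal.

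**3. What 0.049 could do under the other test.** If it came from a two-sided t-test, t = 2.05 on 30 df, and the observed d = 2.05 × √(2/16) = 0.73. In the null trials above:
- with a t-test p of 0.04 to 0.06, Mann-Whitney was at or above 0.05 in 59–68%;
- with a Mann-Whitney p of 0.04 to 0.06, the t-test was at or above 0.05 in 49–66%.

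These shares describe any result that close to the line. They do not show what happened in this trial.

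**4. What baseline adjustment gains.** For ANCOVA of the week-6 value on arm and baseline, the standard error relative to the unadjusted comparison is √(1 − r²), at the price of one degree of freedom (29 instead of 30). The documents do not give r, so these values are assumptions. Power is at d = 0.9, two-sided 0.05, 16 per arm; unadjusted it is 0.69.

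| r (assumed) | √(1 − r²) | SE reduction | Power |
|---|---|---|---|
| 0.3 | 0.954 | 5% | 0.73 |
| 0.5 | 0.866 | 13% | 0.81 |
| 0.7 | 0.714 | 29% | 0.93 |
| 0.8 | 0.600 | 40% | 0.98 |

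Simulated type I error of ANCOVA was 0.050 to 0.051.

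**5. Which way the MMST result would move.** The documents contain no individual data, SDs or correlation, so the adjusted p-value cannot be computed. Simulation used 40,000 trials per setting and r from 0.5 to 0.8. Given an unadjusted p of 0.04 to 0.06, the ANCOVA p was at or above 0.05 in 69–84% of trials with no true effect, and in 6–27% with a true d of 0.72. It can move either way.

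**The case against.** The strongest defence is that the rule is written down and, followed as written, keeps its error rate. That stands: 4.9% to 5.6% is not a serious inflation.

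Second, disagreement near 0.05 is not peculiar to this rule. In a separate simulation (12,000 trials per scenario, 16 per arm, r = 0.7 assumed) of results just under 0.05, the t-test and Mann-Whitney disagreed in 39–55% of trials, and ANCOVA and its rank version in 38–69%. Without that conditioning, the t-test and Mann-Whitney disagreed in only 1.5–2.7% of null trials. This also stands. A single fixed model removes the choice of test; it does not make a borderline result robust.

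Third, the pre-test is not pure noise: at n = 16 it flags exponential data in 72% of samples, though lognormal data in only 42%. The plan's means and medians also allow a crude difference between arms to be read off under either branch. What is missing under both is a confidence interval.

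Fourth, the precision gain depends on correlations that the documents do not give, and restricting MMST at entry to 18–24 would tend to lower the correlation for that outcome. That is fair, and is why the range above starts at 0.3.

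None of this supplies a reason to leave the baseline values out of the comparison between arms.

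**Conclusion.** The point holds as an improvement in efficiency and transparency. It is not a failure of error control. Test selection by Shapiro-Wilk costs little in type I error. Leaving out baseline costs precision, by 5% to 40% of the standard error over assumed correlations of 0.3 to 0.8, probably toward the lower end for MMST.

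A reader might infer that 0.049 is the p-value that decides the trial. The documents do not support this. They name no primary outcome, MMST lies outside the stated purpose of strength and fall risk, and the conclusions on those rest on changes within the training arm. A reader might also infer that the switch produced the significant result. That is not shown either: the test used is not reported, and both tests may fall on the same side of 0.05. What can be said is that the only significant between-arm result is borderline and its test is unnamed.

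Reliance on within-arm tests and the lack of a multiplicity rule are separate and larger matters. They neither cause nor cure this one.

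**What to change.** Use one between-arm analysis for every outcome: ANCOVA of the week-6 value on arm and baseline value, two-sided, reporting the adjusted difference with its 95% confidence interval. Add a rank-based or permutation version as a sensitivity analysis, reported alongside whatever it shows and not used to choose between results. Drop Shapiro-Wilk as the selector.

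Re-report MMST, right and left knee strength, TFES and TUG this way. State which test gave 0.049.

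The cost is new wording in the analysis plan and a re-run on data already held. The document dates the statistical analysis to May 2018 and carries the results itself, so the re-analysis must be labelled post hoc; it cannot be presented as fixed in advance. The sponsor should accept beforehand that the MMST p-value may end on either side of 0.05.
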